8.5.2 Analysis of the secondary variable(s)

8.5.2.1 Analysis methods for secondary efficacy variables

Secondary efficacy variables in this study include:

- Absolute and percentage change from baseline of peripheral blood eosinophil counts until EOT at Visit 10
- Change from baseline in FVC until EOT at Visit 10
- Change from baseline in ACQ-6 score until EOT at Visit 10
- Change from baseline in SGRQ score until EOT at Visit 10

- Change from baseline in FeNO (ppb) until EOT at Visit 10

For each variable, the objective is to determine the effect of benralizumab on the time course of change (onset and maintenance of effect).

Other variables include:

- Change from baseline in Patient Global Impression of Severity until EOT at Visit 10
- Patient and Clinical Global Impression of Change until EOT at Visit 10

For the following variables:

- Peripheral blood eosinophil counts
- Exhaled nitric oxide (FeNO)
- FVC
- ACQ-6 score
- SGRQ
- Change from baseline in PGI-S as a continuous measure.

The change from baseline at each timepoint will be compared between benralizumab and placebo using a repeated measures analysis. The dependent variable will be change from baseline for each endpoint. Treatment group will be fitted as the explanatory variable, region, visit and treatment*visit interaction as fixed effects and corresponding baseline as a covariate. The variance-covariance matrix will be assumed to be unstructured. If the procedure does not converge the compound symmetric variance-covariance matrix will be used instead. The least squares mean for the difference in treatment groups using the interaction between visit and treatment group its 95% CI, and the 2-sided p-values will be reported for each post baseline visit.

As for the primary endpoint the first post baseline timepoint where the p-value for the mean difference between benralizumab and placebo is less than or equal to 0.05 from the repeated measures analysis will be used to determine time to onset of effect. The average over the mean differences between benralizumab and placebo based on the change from baseline (Visit 4) to Days 28 (Visit 8), 56 (Visit 9) and 84 (Visit 10) will be used to determine maintenance of effect. Contrasts will be used to obtain estimates of the average treatment differences over Days 28, 56 and 84 as well as for each timepoint separately.

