The results of the Phase 2b study, MI-CP220 (Castro et al 2014) and the Phase 3 asthma exacerbation studies, SIROCCO (Bleeker et al 2016) and CALIMA (Fitzgerald et al 2016) were used as a basis for the sample sizing. From these studies, it is expected that around 115 patients per treatment arm (230 in total) will provide approximately 90% power for the primary endpoint pre-BD FEV1 with type I error controlled at a two-sided alpha level of 0.05 if the true average over the mean treatment differences (benralizumab – placebo) across Days 28 (Visit 8), 56 (Visit 9), and 84 (Visit 10) is 138 mL. The sample size will also be sufficient to have approximately 80% power for an average over the mean treatment difference of 120 mL. The assumed variability has a within-group standard deviation of 375 mL and within-patient correlation of 0.6. If the within-patient variability is reduced to 350 mL, the sample size would be sufficient 80% power for an average of 110 mL. In addition, it is expected that around 115 patients per treatment arm will have 80% power to detect a true treatment difference (benralizumab – placebo) of 130 mL, assuming a within-group standard deviation of 350 mL or a true treatment difference of 140 mL, assuming a standard deviation of 375 mL. Based on these assumptions, the minimum difference that would be statistically significant at the 5% level ranges from approximately 85 to 100 mL. The sample size was estimated using nQuery + nTerim version 3.0 using methodology by Liu et al (Liu et al 2005).

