#### **4.2.5 Primary outcome variable**

##### **4.2.5.1 Primary analysis**

The change from baseline in pre-BD FEV1 up until the EOT at Visit 10 will be compared between the 30 mg benralizumab group and placebo using a mixed-effect model for repeated measures (MMRM) analysis on patients with a baseline pre-BD FEV1 and at least 1 post-randomization pre-BD FEV1 in the FAS.

The dependent variable will be the change from baseline in pre-BD FEV1 at post-baseline protocol specific visits (up to and including the EOT Visit). Treatment group will be fitted as the explanatory variable, region, visit and treatment\*visit interaction as fixed effects, and baseline pre-BD FEV1 will be fitted as a covariate. The variance-covariance matrix will be assumed to be unstructured. If the procedure does not converge, then a compound symmetric variance-covariance matrix will be used instead. The model is:

$$\text{Change in FEV}_1 = \text{treatment} + \text{baseline pre-BD FEV}_1 + \text{region} + \text{visit} + \text{treatment} * \text{visit}$$

The primary objective of the study is to determine the effect of benralizumab on the time course of change (onset and maintenance of effect) of pre-BD FEV1 using the model described above. The first post-baseline timepoint where the p-value for the mean difference between benralizumab and placebo is  $\leq 0.05$  will be used to determine time to onset of effect. The average over the mean differences between benralizumab and placebo based on the change from baseline (Visit 4) to Days 28 (Visit 8), 56 (Visit 9), and 84 (Visit 10) in pre-BD FEV1 will be used to determine if the study is positive as well as to determine the

maintenance of effect. Contrasts will be used to obtain estimates of the treatment differences over Days 28, 56, and 84, as well as at each timepoint separately.

Results will be presented in terms of least square means (LSMEANS), treatment differences in LSMEANS, 95% confidence intervals (CI) of treatment differences, and p-values at each planned timepoint.

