#### 4.2.5.4 Supportive analyses

The modelled treatment response as well as differences between benralizumab and placebo using the mean change from baseline in pre-BD FEV1 endpoint using an exponential model over time will be estimated. The model will be used to determine the modelled time to onset of effect.

Onset of effect will be defined as: (i) the time taken for benralizumab and placebo to reach a pre-defined change from baseline value, (ii) the time taken for the difference between benralizumab and placebo [change from baseline values to reach a pre-defined value.

As detailed in the study protocol, the main focus is to estimate onset of effect using the primary variable, pre-BD FEV1. Onset of effect will be estimated using change from baseline measurements which were scheduled on days 3, 7, 14, 28, 56, and 84, actual day that data is collected in study is utilized. An exponential relationship will be assumed over time ([Gelman, et al 2013](#)), using Bayesian methodology ([Marostica, et al 2013](#)) to fit a nonlinear mixed effects model to the observed data. The fitted model will then be used to estimate onset of effect for the set of change from baseline values 50, 100, 150, 200, 250, and 300 mL and the set of differences 50, 100, 150, 200, 250, and 300 mL. In addition, an average change from baseline will be estimated for days 1, 3, 7, 14, 21 and 28, 56, 84, and the proportion of subjects with a change from baseline value greater than or equal to {50, 100, 150, 200 and 250 and 300 mL} will be estimated for days 1, 3, 7, 14, 21, 28, 56, 84. Differences between proportions and odds ratios will also be estimated.

It is anticipated that an exponential model will adequately describe pre-BD FEV1 change from baseline over time, based on ([Gelman, et al 2013](#)) and modelling similar data taken from the Phase III SIROCCO and CALIMA trials. However, if the data show that an exponential model is a poor choice, an alternative model will be investigated following the same principles outlined below.

In addition to pre-BD FEV1, one or more secondary variables may also be investigated.

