#### *Missing data descriptions*

Tabular summaries for the percentage of patients by the reason for discontinuation of randomized treatment as well as for withdrawal from the study will be presented by treatment to describe why patients discontinue from randomized treatment or withdraw from the study. The time to discontinuation of randomized treatment and withdrawal from the study will be presented using Kaplan Meier plots (overall and split by treatment related/not treatment

related reason for discontinuation, as defined in Tables 1 and 2). Dependent on these outputs additional exploratory analyses may be produced as deemed necessary to further understand the pattern of missing data.

Primary analysis under the Treatment Policy Estimand using the Missing at Random assumption

The primary analysis of the pre-BD FEV1 is under the treatment policy estimand which allows for differences in outcomes over the entire study treatment period to reflect the effect of initially assigned randomized treatment as well as if subsequent treatments are taken. This primary analysis includes all data until patients withdraw from the study regardless of if they discontinue from randomised treatment. The Mixed Model Repeated Measures model (MMRM) used is a direct likelihood approach (DL) which is valid under the Missing at Random (MAR) assumption.

Sensitivity analysis under the Treatment Policy Estimand using both MAR and MNAR assumptions

To examine the sensitivity of the results of the primary analysis to departures from the underlying assumptions, sensitivity analyses of the repeated measures analyses will be performed for the pre-BD FEV1 using controlled sequential multiple imputation methods based on pattern mixture models, as described in the European Medicines Agency Guideline on Missing Data in Confirmatory Clinical Trials ([EMA 2010](#)). As with the primary analysis, the sensitivity analyses include all data until patients withdrew from the study regardless of if patients discontinue from randomised treatment.

The imputation process consists of a sequence of multiple imputation (MI) steps, where each step is intended to impute missing values at 1 timepoint only. This model will assume that some pre-specified subset of patients who withdraw from the study have correlations with future (unobserved) visits similar to patients in the placebo arm. This allows us to assess various deviations from the MAR assumption.

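### If the unstructured fit fails and FEV1-change variance grows over visits, the compound-symmetry fallback understates the error of the Day 28–84 contrast and overstates it at Day 3

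*SAP*

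**What the plan says.** SAP 4.2.5.1 fits the change from baseline with treatment, region, visit, treatment-by-visit and baseline FEV1. On the covariance it says: "The variance-covariance matrix will be assumed to be unstructured". The only provision for failure is: "If the procedure does not converge, then a compound symmetric variance-covariance matrix will be used instead". Protocol 8.5.1 has the same rule. Protocol 8.5.2.1 repeats it for the secondary variables ("If the procedure does not converge the compound symmetric variance-covariance matrix will be used instead"), SAP 4.2.6.1 carries it over by reference to the primary analysis, and SAP 4.2.8.1 restates it for the plethysmography sub-study.

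The model covers six visits; SAP 4.2.5.4 refers to "change from baseline measurements which were scheduled on days 3, 7, 14, 28, 56, and 84". Two decisions come from it. The average of the Day 28, 56 and 84 differences determines whether the study is positive. Onset is "The first post-baseline timepoint where the p-value for the mean difference between benralizumab and placebo is" at or below 0.05. The estimates come from one fit: "Contrasts will be used to obtain estimates of the treatment differences over Days 28, 56, and 84, as well as at each timepoint separately".

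Neither document names a standard-error or degrees-of-freedom method. SAP 8.1 says that the model "used is a direct likelihood approach (DL) which is valid under the Missing at Random (MAR) assumption".

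**The concern.** An unstructured matrix for six visits has 6 × 7 / 2 = 21 parameters. Compound symmetry has two: one variance and one correlation for every visit from Day 3 to Day 84. If patients' changes spread out with time, the pooled variance is too small for the late visits and too large for the early ones. The primary contrast uses the three latest visits, so its standard error would be understated. Day 3 is the first visit at which onset can be declared, and its standard error would be overstated. One fallback would therefore distort both halves of the primary objective, in opposite directions: too easy a positive study and too late an onset.

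**Working it through.** **Inputs.** From SAP 1.3: 115 patients per arm, SD 375 mL (alternative 350 mL), within-patient correlation 0.6, and "type I error controlled at a two-sided alpha level of 0.05". From SAP 4.2.5.4: six visits. Assumed, because the documents give no visit-specific figures: the SD paths below, linear across the six visits; correlation 0.6 between all pairs; complete data; normal approximation.

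**The plan's own figure.** The SD of a three-visit average is 375 × √((1 + 2 × 0.6)/3) = 321.1 mL. The standard error of the difference is 321.1 × √(2/115) = 42.3 mL. Power at 138 mL is Φ(138/42.3 − 1.96) = 90.3%, which matches the stated figure of about 90%. One SD and one correlation is itself compound symmetry, so under the planning assumptions the fallback is exact.

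**Method.** With balanced data, compound symmetry pools one variance v (the mean of the six visit variances) and one covariance c (the mean of the 15 pairwise covariances).
- Fallback variance of the three-visit average: (v + 2c)/3. Its true variance is the sum of the nine Day 28, 56 and 84 covariance entries, divided by 9.
- Day 3: fallback variance v; true variance is the Day 3 SD squared.
- Standard error of a difference: √(2 × variance/115).
- Actual type I error: 2 × P(Z > 1.96 × fallback SE / true SE).

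**Worked case, SD 300, 320, 340, 360, 380, 400 mL.** v = 123,667 and c = 73,360.
- Primary contrast: the fallback variance is (123,667 + 146,720)/3 = 90,129, SE 39.6 mL. The true variance is (434,000 + 1.2 × 432,800)/9 = 105,929, SE 42.9 mL. The ratio is 0.922 and type I error 7.1%.
- Day 3: fallback SE 46.4 mL, true SE 300 × √(2/115) = 39.6 mL. The ratio is 1.172 and type I error 2.2%. For an assumed true Day 3 difference of 100 mL, power is Φ(100/39.56 − 1.96) = 71.5% with the correct error and Φ((100 − 1.96 × 46.38)/39.56) = 59.1% with the fallback.

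| SD, Day 3 to Day 84 (mL) | SE ratio, primary | Type I, primary | SE ratio, Day 3 | Type I, Day 3 |
|---|---|---|---|---|
| 375 constant | 1.000 | 5.0% | 1.000 | 5.0% |
| 350 to 375 | 0.980 | 5.5% | 1.036 | 4.2% |
| 325 to 375 | 0.959 | 6.0% | 1.078 | 3.5% |
| 300 to 400 | 0.922 | 7.1% | 1.172 | 2.2% |
| 260 to 400 | 0.890 | 8.1% | 1.283 | 1.2% |

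Simulations of 20,000 trials on two other growing paths confirmed both directions. With SD 275 to 375 mL, compound symmetry gave 7.4% (primary) and 1.7% (Day 3); with 225 to 400 mL, 9.5% and 0.6%. Unstructured estimates kept 4.8% to 5.0% on the same data. Letting the correlation decay with lag moved the primary figure by about 0.1 percentage point.

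**Other endpoints, same 300-to-400 mL path restricted to their visits.** The path is in FEV1 units, but only the relative growth matters for the ratio.
- Plethysmography (Days 7 to 84): ratio 0.948, type I 6.3% for the averaged contrast.
- ACQ-6 (Days 14 to 84): ratio 0.974, 5.6%.
- SGRQ (Days 28, 56 and 84 only): the contrast averages every modelled visit, so (v + 2c)/3 equals the true variance and the ratio is 1.000.

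**Is growth plausible from the documents?** SAP 4.2.5.4 models a patient's change as a patient-specific plateau times (1 − e^(−rate × t)) plus error of constant variance. At a common rate the variance of change is σ_C²(1 − e^(−rate × t))² + σ², which rises with t whenever plateaus differ between patients. Taking σ_C² = 0.6 × 375², σ² = 0.4 × 375² and an assumed half-time of 3 days, the SD goes from 278 mL at Day 3 to 375 mL, and type I error is 7.6% (primary) and 1.3% (Day 3). Half-times of 1, 7 and 14 days give 5.4% and 3.7%, 11.0% and 0.9%, and 13.1% and 1.2%. The documents give no half-time, and the SAP also lets the rate vary between patients, so these figures illustrate the premise and do not estimate the effect.

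**The case against.** The strongest reply is that the contingency is remote. Twenty-one covariance parameters over six visits with about 230 patients should converge, and then the fallback never operates. That stands for the primary model. It is weaker in the sub-study, where about 50 patients support 5 × 6 / 2 = 15 parameters and values of unacceptable quality are dropped; but that analysis depends on there being enough acceptable data, and its p-values are nominal.

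Second, the planning text uses a constant SD, under which the fallback is correct. This also stands in part: growth follows from the supportive model's form, but its amount is given nowhere, and mild growth costs the primary contrast only 0.5 to 1.0 percentage point.

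Third, other planned analyses would help to expose a distorted error. SAP 4.2.5.3 includes an ANCOVA on each patient's Day 28, 56 and 84 average, which needs no between-visit covariance (though it uses LOCF). The Bayesian onset model in SAP 4.2.5.4 does not use this fallback. Neither replaces the primary p-value.

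A reader might infer that using the fallback by itself makes the primary p-value too small. The documents do not support that: growing variance is also required. Nor do they support treating all secondary endpoints alike, since the SGRQ average is exact with complete data. Model-based errors are an inference from the direct-likelihood description and the absence of any robust estimator; the SAP does not state them outright.

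**Conclusion.** The point holds as a conditional weakness, at the level of something to consider. It rests on non-convergence, growing variance and model-based errors together. Given all three, primary type I error is about 5.5% to 8.1% and Day 3 type I error about 4.2% to 1.2% over the tabulated SD paths, with correlation 0.6 and complete data. Dropout was not modelled, because the documents give no rate. The averaged contrast is less affected for plethysmography and ACQ-6 and unaffected for SGRQ. Nothing here shows that the primary result is likely to be distorted; the plan simply names a fallback that need not hold its error rate when called on.

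**What to change.** In SAP 4.2.5.1 and 4.2.8.1, and for the secondary endpoints, replace the single fallback with a pre-specified ordered list of structures that allow visit-specific variances, for example heterogeneous Toeplitz and then heterogeneous compound symmetry. The exact order is a matter of preference; fixing it before unblinding is what counts. If plain compound symmetry is ever reached, use empirical (sandwich) standard errors, with a small-sample correction in the sub-study. Sandwich errors should come last because they repair the standard error but not the likelihood's reliance on a correct covariance when data are missing at random. State the standard-error method explicitly. Record the departure from Protocol 8.5.1 and 8.5.2.1 in SAP section 6.

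The cost is a short edit in a few places and possibly slightly wider intervals. Nothing changes if the unstructured fit converges.

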#### **4.2.5.2 Sensitivity analysis**

A sensitivity analysis of pre-BD FEV1 may be performed as applicable by excluding patients who meet at least one of situations below:

- Who do not withhold their regular asthmas medication prior to spirometry assessment
- Who do not withhold their SABA for more than 6 hours prior to spirometry assessment

#### **4.2.5.3 Subgroup analysis**

To explore the uniformity of the detected overall treatment effect on the primary efficacy variable, subgroup analyses, including statistical modelling where the interaction between treatment and covariates to estimate the treatment effect within each subgroup, may be performed for the following factors for maintenance of effect: OCS use at baseline (yes/no), gender, race, age group categories (<65, ≥65 years), geographic region, BMI (≤35, >35 kg/m^2), the number of exacerbations during the previous year (2, ≥3 exacerbations), nasal polyps (yes/no), baseline immunoglobulin E (IgE) concentration (<150kU/L, ≥150kU/L), baseline EOS and FeNO. In addition, an overall standardized effects plot and forest plot across all subgroups will be produced for maintenance of effect. ANCOVA will be utilized in the overall standardized effects plot to assure convergence and avoid run-time issue. Average value from Day 28, 56 and 84 will be the response variable. Treatment group and baseline pre-BD FEV1 will be included in the model for overall effect model. Treatment group, subgroup being evaluated, interaction of treatment group and subgroup being evaluated, and baseline pre-BD FEV1 will be included in the subgroup effect model. Missing data will be imputed by last observation carried forward (LOCF) prior to the average of Day 28, 56 and 84 is derived.

Additionally, subgroup analysis of pre-BD FEV1 will be performed to explore the relationship with baseline blood eosinophil counts using the categories ≥300-449/μL and ≥450/μL, and with baseline FeNO using the categories of ≤50 and >50 ppb. Blood eosinophil data collected at Screening visit will be used for this categorization to ensure that all subjects can be classified and included in the summary.

It is important to note that the study has not been designed or powered to assess efficacy within any of these pre-defined subgroups, and as such, these analyses are considered exploratory.

#### 4.2.5.4 Supportive analyses

The modelled treatment response as well as differences between benralizumab and placebo using the mean change from baseline in pre-BD FEV1 endpoint using an exponential model over time will be estimated. The model will be used to determine the modelled time to onset of effect.

Onset of effect will be defined as: (i) the time taken for benralizumab and placebo to reach a pre-defined change from baseline value, (ii) the time taken for the difference between benralizumab and placebo [change from baseline values to reach a pre-defined value.

As detailed in the study protocol, the main focus is to estimate onset of effect using the primary variable, pre-BD FEV1. Onset of effect will be estimated using change from baseline measurements which were scheduled on days 3, 7, 14, 28, 56, and 84, actual day that data is collected in study is utilized. An exponential relationship will be assumed over time ([Gelman, et al 2013](#)), using Bayesian methodology ([Marostica, et al 2013](#)) to fit a nonlinear mixed effects model to the observed data. The fitted model will then be used to estimate onset of effect for the set of change from baseline values 50, 100, 150, 200, 250, and 300 mL and the set of differences 50, 100, 150, 200, 250, and 300 mL. In addition, an average change from baseline will be estimated for days 1, 3, 7, 14, 21 and 28, 56, 84, and the proportion of subjects with a change from baseline value greater than or equal to {50, 100, 150, 200 and 250 and 300 mL} will be estimated for days 1, 3, 7, 14, 21, 28, 56, 84. Differences between proportions and odds ratios will also be estimated.

It is anticipated that an exponential model will adequately describe pre-BD FEV1 change from baseline over time, based on ([Gelman, et al 2013](#)) and modelling similar data taken from the Phase III SIROCCO and CALIMA trials. However, if the data show that an exponential model is a poor choice, an alternative model will be investigated following the same principles outlined below.

In addition to pre-BD FEV1, one or more secondary variables may also be investigated.

As described in the protocol, measurements for pre-BD FEV1 will be recorded on day 0, 3, 7, 14, 28, 56, 84. For every subject, pre-BD FEV1 change from baseline values will be calculated for day 3, 7, 14, 28, 56, 84. If a baseline value or post-baseline measurement is missing, the corresponding change from baseline value will be set to missing. Onset of effect will be estimated for subjects in the full analysis set (FAS) with a baseline value and at least one pre-BD FEV1 measurement recorded after the first dose of study drug.

